13.0 STATISTICAL CONSIDERATIONS

This is an open label multicentre phase II trial to evaluate the anti-tumour activity of CFI-400945 when given with durvalumab by determining the objective response rate in patients as defined in Section 4.1.1. A 2-stage Simon minimax design will be used.

13.1 Primary Endpoints and Analysis

The primary endpoint of this study is objective response rate, which will be estimated by the proportion of evaluable patients who had complete response (CR) or partial response (PR) as their best response as assessed by RECIST 1.1 criteria. The exact 95% confidence interval for the response rate will be calculated. The median and range of the duration of response, defined as the time from date of CR or PR to the date when progression or death is observed, will be estimated based on Kaplan-Meier method.

Secondary objectives include Disease Control Rate (DCR, defined as CR or PR or stable disease (SD) > 16 weeks in duration) which will be analyzed similarly as objective response rate, as well as response rate determined by iRECIST.

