1.2 Secondary Objectives

- To evaluate Disease Control Rate (DCR, defined as CR or PR or stable disease (SD) > 16 weeks in duration) of CFI-400945 given with durvalumab.
- To evaluate the immune-related response rate (iRECIST) of CFI-400945 given with durvalumab.
- To establish the safety and tolerability of CFI-400945 given orally in combination with durvalumab in a q4w schedule and to confirm the recommended phase II dose (RP2D) in patients with metastatic triple negative breast cancer (TNBC).

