- 1 Adverse events felt to be related to protocol therapy will be followed until resolved to \leq Grade 2. Reversible durvalumab- related adverse events \geq grade 3 should be followed until resolved to baseline grade including related toxicity that occurs in the follow up period. Irreversible events may not need to be followed. Contact CCTG to discuss. Adverse Events to be evaluated using the NCI Common Terminology Criteria for Adverse Events (CTCAE v5.0) (see Appendix V).
- 2 Height is only required at baseline.
- 3 Hematology is to be done twice weekly cycles 1 and 2. Provided patient has not experienced grade 3 or 4 neutropenia, hematology can be done weekly cycle 3 onward. For patients on for 6+ cycles, contact CCTG for a waiver if appropriate. See section 7 for additional monitoring of patients with toxicity.
- 4 Required at 4 weeks. To be done additionally every 3 months thereafter to follow abnormal lab results felt related until resolved to \leq Grade 2.
- 5 If creatinine $> 1.5 \times$ ULN, calculated CrCl is required and must meet eligibility criteria for re-treatment. For patients who have discontinued CFI-400945 and are continuing on durvalumab alone, criteria for creatinine clearance may be lower. Please contact CCTG to discuss.
- 6 Required at baseline then as clinically indicated. It is preferable that both amylase and lipase parameters are assessed. For sites where only 1 of these parameters is routinely measured then either lipase or amylase is acceptable.
- 7 Free T3 and free T4 will be measured if TSH is abnormal.
- 8 For women of childbearing potential only (urine or serum test). Within 72 hours prior to enrollment. Pregnancy test (in women of childbearing potential), as part of Pre-Study Evaluation, may include an ultrasound to rule-out pregnancy.
- 9 As clinically indicated in WOCBP.
- 10 Required at baseline then as clinically indicated.
- 11 Bone scan is required at baseline for all patients. Thereafter, bone scan is only required to be repeated if positive at baseline to confirm CR/iCR, PR/iPR or SD/iSD, and/or when PD is suspected and as clinically indicated.
- 12 To ensure comparability, baseline scans and subsequent scans to assess response must be performed using identical technique (i.e. scans performed immediately following bolus contrast administration using a standard volume of contrast, the identical contrast agent, and preferably the same scanner). Maintain schedule every 8 weeks, even if cycles are delayed.

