7.0 TREATMENT PLAN

Although the Canadian Cancer Trials Group acts as the coordinating agency for the trial, the responsibility for treatment of patients rests with the individual investigator.

In accordance with CCTG policy, protocol treatment is to begin within 2 working days of patient enrollment.

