PR	Non-PD/ not all evaluated	No	PR	
SD	Non-PD/ not all evaluated	No	SD	Documented at least once ≥ 4 wks. from baseline*
Not all evaluated	Non-PD	No	NE	
PD	Any	Any	PD	
Any	PD	Any	PD	
Any	Any	Yes**	PD	
Non target lesions ONLY				
No Target	CR	No	CR	Normalization of tumour markers, tumour nodes < 10 mm
No Target	Non-CR/non-PD	No	Non-CR/non-PD	
No Target	Not all evaluated	No	NE	
No Target	Unequivocal PD	Any	PD	
No Target	Any	Yes	PD	

Note: Patients with a global deterioration of health status requiring discontinuation of treatment without objective evidence of disease progression at that time should be reported as “symptomatic deterioration”. This is a reason for stopping therapy, but is NOT objective PD. Every effort should be made to document the objective progression even after discontinuation of treatment.
 
* For this study, baseline is defined as the date of enrollment.
 
** Investigators should record all new lesions; if the new lesion is felt to be equivocal, treatment may be continued pending further assessments – see Table 2.
				

For non randomized trials, where confirmation of response is required, best overall response can be interpreted as follows:

Response: First Time Point	Subsequent Time Point	BEST Overall Response	Also Requires
CR	CR	CR	Normalization of tumour markers, tumour nodes < 10 mm
CR	PR	SD, PD or PR (see comment*)	
CR	SD	SD provided minimum criteria for SD duration met, otherwise, PD	
CR	PD	SD provided minimum criteria for SD duration met, otherwise, PD	
CR	NE	SD provided minimum criteria for SD duration met, otherwise NE	
PR	CR	PR	
PR	PR	PR	
PR	SD	SD	
PR	PD	SD provided minimum criteria for SD duration met, otherwise, PD	
PR	NE	SD provided minimum criteria for SD duration met, otherwise NE	
NE	NE	NE	
* may consider PR providing initial “CR” likely PR on subsequent review – then original CR should be corrected. Recurrence of lesion after true CR is PD.			

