8.5 Stable Disease Duration

Stable disease duration will be measured from the time of start of treatment until the criteria for progression are met, taking as reference the smallest sum on study (including baseline).

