8.6 Methods of Measurement

The same method of assessment and the same technique should be used to characterize each identified and reported lesion at baseline and during follow-up. Assessments should be identified on a calendar schedule and should not be affected by delays in therapy, which may be treatment arm dependent. While on study, all lesions recorded at baseline should have their actual measurements recorded at each subsequent evaluation, even when very small (e.g. 2 mm). If it is the opinion of the radiologist that the lesion has likely disappeared, the measurement should be recorded as 0 mm. If the lesion is believed to be present and is faintly seen but too small to measure, a default value of 5 mm should be assigned. For lesions which fragment/split add together the longest diameters of the fragmented portions; for lesions which coalesce, measure the maximal longest diameter for the “merged lesion”.

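### The DCR cut-off for stable disease coincides with the second 8-weekly scan, so patients who progress at that scan count as controlled or not according to the day it is done

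*Combined protocol and SAP*

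**What the plan says.** Sections 1.2 and 13.1 define disease control as a complete response, a partial response, or stable disease lasting strictly more than 16 weeks: "DCR, defined as CR or PR or stable disease (SD) > 16 weeks in duration". DCR is to be analysed in the same way as the response rate, as a proportion of evaluable patients with an exact 95% interval.

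Section 8.5 gives the clock for stable disease: "Stable disease duration will be measured from the time of start of treatment until the criteria for progression are met". The duration therefore ends on the date of progression, not on the date of the last scan that showed stability.

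Tumour imaging is every 8 weeks. Footnote 12 to the Section 5.0 flowsheet says "Maintain schedule every 8 weeks, even if cycles are delayed", and Section 8.6 says "Assessments should be identified on a calendar schedule and should not be affected by delays in therapy".

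Table 1 in Section 8.2.5 sets the minimum for stable disease as best response: "Documented at least once ≥ 4 wks. from baseline". Its footnote adds "For this study, baseline is defined as the date of enrollment". Section 7.0 says "protocol treatment is to begin within 2 working days of patient enrollment".

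We found no window for on-study scans, no rule assigning scans to nominal visits, and no requirement for a progression-free scan at or after week 16. The tolerances in Section 5.0 that lie nearest concern blood draws and physical examinations.

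**The concern.** Two 8-week intervals make 16 weeks, so the threshold falls on a scheduled scan. A patient who is stable at week 8 and progresses at the second scan has met the minimum for stable disease. Whether that patient also has more than 16 weeks of it depends on the day the second scan took place. The radiological evidence is the same either way: one stable scan at week 8, then progression.

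The first-listed secondary endpoint would then reflect appointment timing as well as drug activity, and late scans would raise it. The trial is open-label and single-arm, without central radiology review, so a classification rule is better fixed before the data are seen.

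**Working it through.** **The plan's own figures.** The plan gives no target, null rate or power for DCR. Its only design figures concern the response rate in Section 13.2 (15 then 28 patients, stop at 2 or fewer, reject at 8 or more). An exact two-stage binomial calculation reproduces them: type I error 0.046 at a true rate of 15%, against the stated 5%, and power 0.803 at 35%, against the stated 0.80. DCR does not enter that rule.

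**Day arithmetic.** Inputs: 8-weekly scans (Sections 5.0 and 8.6), a threshold of more than 16 weeks (Sections 1.2 and 13.1), and duration from treatment start to progression (Section 8.5).

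- Second scan: 2 × 8 × 7 = day 112. Threshold: 16 × 7 = 112 days.
- Duration = 112 + days late − days from scan-clock origin to treatment start. The patient counts as controlled if this exceeds 112.

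The documents do not say whether the 8-week clock starts at treatment or at enrollment. Two working days can be up to about 4 calendar days over a weekend, so the flip point is:

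| Treatment starts this long after the clock origin | Still a failure | First counted as control |
|---|---|---|
| 0 days | on time (day 112) | 1 day late (day 113) |
| 1 day | 1 day late | 2 days late |
| 2 days | 2 days late | 3 days late |
| 4 days | 4 days late | 5 days late |

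**Size without a model.** One reclassified patient moves DCR by 1/28 = 3.6 points, or 1/15 = 6.7 points if the trial stops at stage 1. As an illustration, assume 8 of 28 patients with disease control: 28.6% (exact 95% interval 13.2 to 48.7). One added patient gives 9/28 = 32.1% (15.9 to 52.4). Three give 11/28 = 39.3% (21.5 to 59.4).

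**Size under assumptions not in the documents.** Take exponential time to progression with median m weeks, found only at scheduled scans. The share progressing between weeks 8 and 16 is 2^(−8/m) − 2^(−16/m):

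- m = 8: 0.500 − 0.250 = 0.250, × 28 = 7.0 patients
- m = 12: 0.233, × 28 = 6.5 patients
- m = 16: 0.707 − 0.500 = 0.207, × 28 = 5.8 patients

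Excess DCR over the rule of no progression at scan 2 is about this share times the chance that scan 2 falls after day 112. With whole-day scan dates scattered normally around day 112, that chance is 1 − Φ(0.5/3) = 0.434 for an SD of 3 days and 1 − Φ(0.5/5) = 0.460 for 5 days. The product runs from 0.207 × 0.434 = 0.090 to 0.250 × 0.460 = 0.115. Simulation with scatter on both scans gives:

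- no mean shift: 9 to 12 points
- scan 2 on average 3 days early: 3 to 6 points
- scan 2 on average 3 days late: 16 to 21 points

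The early case is also close to what an enrollment-based clock would produce if treatment starts about 3 days later. In every setting the excess is positive, because the literal rule can only add patients who progressed at scan 2.

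**The case against.** Several points on the other side have force.

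- On a schedule kept to the day, the strict inequality already gives the sensible answer: progression on or before day 112 fails. Nothing in the documents suggests that scans run late on average. This stands, but there is no window either, and a scan a few days late is ordinary.
- One day late is exact only if the scan clock starts at treatment. The only baseline date the plan defines is enrollment, and on that clock the flip needs a scan 2 to 5 days late. This stands, and it moves the likely size towards the lower range.
- The percentages rest on assumed progression times and scan scatter. The model also ignores routes to earlier detection: clinical tumour measurements on Day 1 of each cycle, clinically documented progression (Section 10.2), and the earlier date for equivocal progression later confirmed (Section 8.2.5). It also ignores confirmed responders, who count in any case. All of these shrink the affected group.
- Anchoring to a windowed scan changes the endpoint slightly: stability seen a few days before day 112 would count. That is a real cost, accepted below.

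A reader might also infer the converse, that a patient still stable on a day-110 scan with no later scan fails because fewer than 16 weeks were recorded. The documents do not support this. Section 8.5 ends the duration at progression, so it is still open on day 110. Scans continue 8-weekly, and Section 10.4 requires 3-monthly follow-up until relapse for patients who stop treatment with stable disease. For a patient lost straight after scan 2, the plan has no rule. That is a gap in the text, not a stated failure.

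**Conclusion.** The concern holds. As written, a patient with stable disease at week 8 and first progression at scan 2 is a DCR failure or a DCR success depending on whether that scan falls after day 112 from treatment start. This follows from the documents alone. So does the direction: relative to no progression at the week-16 scan, the rule can only raise DCR, by 3.6 points per patient in 28.

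The overall size is less certain. Roughly 3 to 12 points, and up to about 21 with scans 3 days late, depends on exponential progression, the chosen medians and the chosen scan scatter, none of which the plan gives.

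It would be wrong to infer that the trial's conclusion is at risk. DCR has no hypothesis, threshold or decision rule, and stopping and rejection depend on response rate only. One or two reclassified patients would also stay well inside the exact interval. This is a change that should be made to a descriptive secondary endpoint, not a flaw in the design.

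**What to change.** In Sections 1.2 and 13.1, with a cross-reference to Section 8.5, define DCR as confirmed complete or partial response, or stable disease with no RECIST 1.1 progression up to and including the nominal week-16 assessment (the second on-study scan). State also:

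- where the scan clock starts, treatment or enrollment
- a fixed window for that assessment, for example 1 week either side
- that progression at that assessment is no disease control whatever the day, and stable disease at an in-window scan is disease control
- that if the scan is missed or out of window, a later scan without progression counts as control, and otherwise the patient counts as not controlled

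The cost is wording in two sections and a cross-reference, with no new scans, visits or patients. The reported DCR will usually be somewhat lower, and stable disease at a slightly early in-window scan will count as control although just under 16 weeks have elapsed.

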13.2 Sample Size and Duration of Study

A 2-stage Simon minimax design will be used.

For sample size estimation, a response rate of 0.15 to monotherapy is assumed. The null hypothesis that the true response rate is 15% or less will be tested against a one-sided alternative. In the first stage, 15 patients will be accrued. If 2 or less responses are observed, the study will be stopped. Otherwise, accrual will continue to a total of 28. The null hypothesis will be rejected if 8 or more responses are observed in 28 patients. This design yields a type I error rate of 5% and power of 0.8 when the true response rate is 35%.

13.3 Safety Monitoring

Adverse events will be monitored on an ongoing basis by the central office and their frequencies reported semi-annually at investigators' meetings. A safety review after the enrollment of 6 patients, who have received at least 1 cycle and up to 3 cycles, will be conducted prior to reopening to further accrual.

14.0 PUBLICATION POLICY

14.1 Authorship of Papers, Meeting Abstracts, Etc.

14.1.1 The results of this study will be published. Prior to trial activation, the chair will decide whether to publish the trial under a group title, or with naming of individual authors. If the latter approach is taken, the following rules will apply:

- The first author will generally be the chair of the study.
- A limited number of the members of the Canadian Cancer Trials Group may be credited as authors depending upon their level of involvement in the study.
- Additional authors, up to a maximum of 15, will be those who have made the most significant contribution to the overall success of the study. This contribution will be assessed, in part but not entirely, in terms of patients enrolled and will be reviewed at the end of the trial by the study chair.

14.1.2 In an appropriate footnote, or at the end of the article, the following statement will be made:

“A study supported and coordinated by the Canadian Cancer Trials Group. Participating investigators included: (a list of the individuals who have contributed patients and their institutions). Research supported by AstraZeneca and University Health Network.”

14.2 Responsibility for Publication

It will be the responsibility of the Study Chair/s to write up the results of the study within a reasonable time of its completion. If after a period of six months following study closure the manuscript has not been submitted, the central office reserves the right to make other arrangements to ensure timely publication.

Dissemination of Trial Results

CCTG will inform participating investigators of the primary publication of this trial. The complete journal reference and, if where publicly available, the direct link to the article will be posted on the Clinical Trial Results public site of the CCTG web site (<http://www.ctg.queensu.ca>).

14.3 Submission of Material for Presentation or Publication

Material may not be submitted for presentation or publication without prior review by the CCTG Senior Investigator, Senior Biostatistician, Study Coordinator, and approval of the Study Chair. Individual participating centres may not present outcome results from their own centres separately. Supporting groups and agencies will be acknowledged.

15.0 ETHICAL, REGULATORY AND ADMINISTRATIVE ISSUES

15.1 Regulatory Considerations

All institutions in Canada must conduct this trial in accordance with International Conference on Harmonization-Good Clinical Practice (ICH-GCP) Guidelines.

This trial is being conducted under a Clinical Trial Application (CTA) with Health Canada. As a result, the conduct of this trial must comply with Division 5 of the Canadian Regulations Respecting Food and Drugs (Food and Drugs Act).

15.2 Inclusivity in Research

CCTG does not exclude individuals from participation in clinical trials on the basis of attributes such as culture, religion, race, national or ethnic origin, colour, mental or physical disability (except incapacity), sexual orientation, sex/gender, occupation, ethnicity, income, or criminal record, unless there is a valid reason (i.e. safety) for the exclusion.

In accordance with the Declaration of Helsinki and the Tri-Council Policy Statement (TCPS), it is the policy of CCTG that vulnerable persons or groups will not be automatically excluded from a clinical trial (except for incompetent persons) if participation in the trial may benefit the patient or a group to which the person belongs.

However, extra protections may be necessary for vulnerable persons or groups. It is the responsibility of the local investigator and research ethics board (REB) to ensure that appropriate mechanisms are in place to protect vulnerable persons/groups. In accordance with TCPS, researchers and REBs should provide special protections for those who are vulnerable to abuse, exploitation or discrimination. As vulnerable populations may be susceptible to coercion or undue influence, it is especially important that informed consent be obtained appropriately.

Centres are expected to ensure compliance with local REB or institutional policy regarding participation of vulnerable persons/groups. For example, if a vulnerable person/group would be eligible for participation in a CCTG clinical trial under this policy but excluded by local policy, it is expected that they would not be enrolled in the trial. It is the centre's responsibility to ensure compliance with all local SOPs.

It is CCTG's policy that persons who cannot give informed consent (i.e. mentally incompetent persons, or those physically incapacitated such as comatose persons) are not to be recruited into CCTG studies. It is the responsibility of the local investigator to determine the subject's competency, in accordance with applicable local policies and in conjunction with the local REB (if applicable).

Subjects who were competent at the time of enrollment in the clinical trial but become incompetent during their participation do not automatically have to be removed from the study. When re-consent of the patient is required, investigators must follow applicable local policies when determining if it is acceptable for a substitute decision maker to be used. CCTG will accept re-consent from a substitute decision maker. If this patient subsequently regains capacity, the patient should be re-consented as a condition of continuing participation.

15.3 Obtaining Informed Consent

It is expected that consent will be appropriately obtained for each participant/potential participant in a CCTG trial, in accordance with ICH-GCP section 4.8. The centre is responsible for ensuring that all local policies are followed.

Additionally, in accordance with GCP 4.8.2, CCTG may require that participants/potential participants be informed of any new information that may impact a participant's/potential participant's willingness to participate in the study.

Based upon applicable guidelines and regulations (Declaration of Helsinki, ICH-GCP), a participating investigator (as defined on the participants list) is ultimately responsible, in terms of liability and compliance, for ensuring informed consent has been appropriately obtained. CCTG recognizes that in many centres other personnel (as designated on the participants list) also play an important role in this process. In accordance with GCP 4.8.5, it is acceptable for the Qualified Investigator to delegate the responsibility for conducting the consent discussion.

CCTG requires that each participant sign a consent form prior to their enrollment in the study to document his/her willingness to take part. CCTG may also require, as indicated above, that participants/potential participants be informed of new information if it becomes available during the course of the study. In conjunction with GCP 4.8.2, the communication of this information should be documented.

CCTG allows the use of translators in obtaining informed consent. Provision of translators is the responsibility of the local centre. Centres should follow applicable local policies when procuring or using a translator for the purpose of obtaining informed consent to participate in a clinical trial.

In accordance with ICH-GCP 4.8.9, if a subject is unable to read then informed consent may be obtained by having the consent form read and explained to the subject.

